**Title: Dose of Vestibular Rehabilitation Required for Clinical Improvements in Individuals With Vestibular Hypofunction**

**NCT04851184**

**Date Approved: 11/13/23**

**Protocol and Statistical Analysis Plan.**

**Description:**

When a potential subject is identified, the subject will be screened for appropriateness of inclusion for this study. The screen will include: questions regarding history of concussion, questions related to type of vestibular symptoms (dizziness, room spinning, imbalance, etc.), an oculomotor screen for gaze and spontaneous nystagmus, a Head Impulse Test, and a Dynamic Visual Acuity Test. Subjects will be excluded if they have a gaze nystagmus in room light, a convergence disorder detected with oculomotor screening, or are currently enrolled in vision therapy, as an adjunct treatment. These findings would indicate that the patient's diagnosis falls in a category not included in this study, or that visual disturbances would be a confounding factor during this study. If, following screening, the potential subject is determined to be appropriate for this study, informed consent will be obtained after the potential subject has all their questions answered to their satisfaction.

After informed consent has been obtained from a recruited subject, those with Unilateral Vestibular Hypofunction (UVH) will be asked to perform a 4-week intervention, while those with Bilateral Vestibular Hypofunction (BVH) or those post-concussion will each be asked to perform a 12-week intervention. Those with UVH will undergo a shorter intervention due to strong evidence that neural adaptation occurs much more quickly (usually 4 weeks) than those with BVH and history of concussion. The intervention will consist of physical therapy visits combined with a home program of specific vestibular exercises. Each subject will be asked to attend physical therapy visits at least one time per week throughout the 4- or 12-week period.

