Assessments will be performed on all groups and consist of a combination of vestibulo-ocular assessment, balance and clinical functional outcome measures, a survey regarding the usability of the virtual reality device, and surveys of subject satisfaction (see table below). Balance and functional outcome measures will include the Dizziness Handicap Inventory (DHI), Visual Analog Score (VAS) of symptoms, Visual Vertigo Analogue Scale, Functional Gait Assessment (FGA), Activities-Specific Balance Confidence (ABC) Scale, and the modified Clinical Test of Sensory Organization and Balance (CTSIB). Vestibulo-ocular assessment will be conducted using Frenzel goggles and will include tests of: Spontaneous Nystagmus, Gaze-evoked Nystagmus, Smooth Pursuit, Doll's Eyes, Head Impulse, Dynamic Visual Acuity, and Dix-Hallpike. Subjects will also perform the X1 vestibulo-ocular reflex exercise using the virtual reality device for a maximum of 30 seconds in incrementing levels. The X1 involves focusing on a stationary letter while

moving the head back and forth or up and down at approximately 1 cycle per second. If at any point the patient experiences an increase of 3 points on a scale of 0 (no dizziness) to 10 (worst imaginable) of symptoms, exercise in the device will stop. For instance, if a subject begins with a rating of 1/10 dizziness, they are instructed to stop if their symptoms reach a 4/10 or greater. Additionally, at weeks 4, 8 and 12, surveys would ask about patient comfort and level of satisfaction with regards to the intervention protocol. At the conclusion of their participation, subjects will be asked to complete the System Usability Scale to determine the usability of the virtual reality device. On each day of testing, subjects are free to skip any tests or questions they do not want to perform.

Subjects are randomly assigned to the usual rehabilitation or intervention group based on each of the following diagnostic categories: Unilateral Vestibular Hypofunction, Bilateral Vestibular Hypofunction, and post-Concussion. Therefore, there will be a total of three (3) usual rehabilitation and three (3) intervention groups (see table below). Additionally, there will be a seventh group consisting of healthy control subjects that have no history of vestibular symptoms.

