Per patient and therapist discretion, additional physical therapy visits may be scheduled to aid in patient understanding of exercise progression protocol, assess correct performance of exercise (with or without virtual reality device). Non-study related physical therapy visits may be scheduled between sessions in order to address impairments unrelated to vestibulo-ocular deficits. These may include interventions to address musculoskeletal deficits or other balance related impairments. Any additional sessions of physical therapy will be reported in order to determine possible confounding information.

There will be an additional group of healthy control subjects that will be tested for only one day. Healthy subjects will be recruited through flyers, approved email lists, and word of

mouth in the general public. This healthy control group will perform the same tests as the other groups perform on Day 1. This group will be used to compare outcomes of usual rehabilitation and intervention groups, to the function of those without disorders of vestibular function.

Statistical Analysis Plan:

Similarities in subject group characteristics will be determined using a one-way ANOVA. Characteristics will include: Age, height, weight, questionnaire scores, and functional outcome scores. A two-way Repeated-Measures ANOVA will be used for analysis of functional outcomes measures for each assessment time (0,4,8, and 12 weeks) for each group of Unilateral Vestibular Hypofunction, Bilateral Hypofunction Dysfunction, and Post Concussion Syndrome compared to their respective controls. A one-way ANOVA will be used to compare functional outcome measures of all groups on the final day of treatment only to healthy control performance. A multiple regression analysis will be used to determine the relationship between the exercise parameters and changes in outcome measures.

Group	Subgroup	Home Program Intervention	Visits	Test performed by all groups
Unilateral Vestibular Hypofunction	Usual rehabilitation	Usual Physical Therapy with patient self-reported compliance log	1) Initial Evaluation 2) 4-Weeks post	Questionnaires  Dizziness Handicap Inventory Activities-Specific Balance Confidence Scale  Visual Vertigo Analog Scale  Visual Analog Score of symptoms
	Intervention	Home exercises using Virtual Reality Vestibular Rehabilitation	1) Initial Evaluation 2) 4-Weeks post	  Functional Assessment

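### The SAP does not say how non-sphericity will be handled in the four-visit BVH and post-concussion ANOVAs; an uncorrected arm-by-time F test could run at about 5.5–9% at an assumed 5% level

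*Combined protocol and SAP*

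**What the plan says.** The Statistical Analysis Plan section gives one sentence to the between-arm analysis over time: "A two-way Repeated-Measures ANOVA will be used for analysis of functional outcomes measures for each assessment time (0,4,8, and 12 weeks"). By the same sentence, the comparison is made separately within the three diagnoses, each against its own controls. The Description section provides for "there will be a total of three (3) usual rehabilitation and three (3) intervention groups", so each diagnosis has two randomised arms, and the controls in that sentence are most naturally the usual-rehabilitation arms.

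The number of visits differs by diagnosis. The Description says that "those with Bilateral Vestibular Hypofunction (BVH) or those post-concussion will each be asked to perform a 12-week intervention", and the visit table lists an initial evaluation and visits at 4, 8 and 12 weeks for both of these. It also says that "those with Unilateral Vestibular Hypofunction (UVH) will be asked to perform a 4-week intervention", and the table lists only an initial evaluation and a 4-week visit for UVH.

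The documents do not mention sphericity, Mauchly's test, a Greenhouse-Geisser or Huynh-Feldt adjustment, a multivariate test or a mixed model. They also do not say that the F test will be left uncorrected. They state no significance level, sample size, standard deviations or between-visit correlations.

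**The concern.** With four visits the arm-by-time effect has 3 numerator degrees of freedom, and the univariate F test pools the within-subject error over all visits. The pooled F has its nominal error rate only under sphericity.

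There is reason to doubt sphericity here. Visits span 12 weeks, and the Description has patients progress duration, speed, background and posture at their own pace as symptoms allow. If patients recover at different rates, adjacent visits will tend to correlate more than visits 12 weeks apart. Pre-treatment scores may also correlate less with follow-up than follow-ups do with each other. This is a reasoned expectation; the documents contain no data on it.

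The arm-by-time test is where an effect of the virtual reality program would show. If sphericity fails and nothing is corrected, its p-values are too small. There is a second cost: corrected, uncorrected and multivariate results all fit the SAP sentence and can disagree near the threshold, so the choice could be made after the results are seen.

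**Working it through.** The plan gives no error rate, power or sample size, so there is no figure to reproduce.

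**Inputs from the documents.** Two arms per diagnosis; k = 4 visits in BVH and post-concussion; k = 2 in UVH.

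**Inputs assumed.** Level 0.05; equal allocation; n = 10, 20 or 40 per arm in the table below, with supporting runs from n = 8; normal data, nothing missing, no true arm-by-time effect; the covariance patterns listed.

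**Step 1: what unequal correlation does.** Take unit SDs and serial correlation 0.9 per 4 weeks. The variance of the difference between two visits is 2(1 − r):
- 4 weeks apart: 2(1 − 0.9) = 0.20
- 8 weeks apart: 2(1 − 0.81) = 0.38
- 12 weeks apart: 2(1 − 0.729) = 0.542

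Sphericity needs these to be equal. The pooled error corresponds to their average over the six visit pairs: (3×0.20 + 2×0.38 + 0.542)/6 = 0.317.

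**Step 2: measure the departure.** With λ the variances of the k − 1 orthonormal visit contrasts (eigenvalues), Box's epsilon is ε = (Σλ)² / [(k − 1)Σλ²]. It is 1 under sphericity and 1/3 at worst for k = 4. Example: baseline correlates 0.4 with later visits, and later visits correlate 0.9 with each other.
- Two contrasts among later visits: 1 − 0.9 = 0.10 each
- Baseline against the later mean: (9 + 3 + 6×0.9 − 18×0.4)/12 = 10.2/12 = 0.85
- ε = 1.05² / [3(0.7225 + 0.01 + 0.01)] = 1.1025/2.2275 = 0.495

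**Step 3: error rate.** The uncorrected test refers F to 3 and 3(2n − 2) degrees of freedom. Greenhouse-Geisser multiplies both by the estimated ε. Results from 40,000 simulated null trials per setting, as ranges over n = 10, 20 and 40 (simulation standard error near 5%: √(0.05×0.95/40,000) ≈ 0.11 percentage points):

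| Assumed visit pattern | ε | Uncorrected | Greenhouse-Geisser |
|---|---|---|---|
| Equal correlations (0.5 or 0.7) | 1.00 | 4.7–5.1% | 3.8–4.9% |
| Random slopes, small | 0.96 | 5.2% | 4.2–4.7% |
| Serial, 0.5 | 0.86 | 5.5–5.9% | 4.4–4.9% |
| Serial, 0.7 | 0.77 | 6.2–6.3% | 4.5–4.8% |
| Baseline 0.5, later visits 0.8 | 0.73 | 6.2–6.7% | 4.4–4.9% |
| Random slopes, moderate | 0.71 | 6.7–6.8% | 4.7–4.9% |
| Serial, 0.9 | 0.68 | 7.0–7.2% | 4.9% |
| Random slopes, large | 0.56 | 7.7–8.2% | 4.8–5.2% |
| Baseline 0.4, later visits 0.9 | 0.50 | 8.5–8.7% | 4.9–5.1% |

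Supporting runs at 8 to 20 per arm (20,000 trials per setting) agree: 5.6–7.0% with serial correlation 0.5–0.9, and 8.7–9.1% in the last pattern. The multivariate test held 4.8–5.2% in every tabulated pattern.

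**Step 4: bound.** At ε = 1/3 the size is P(F(1, 2n − 2) > critical F(3, 3(2n − 2))). For n = 10 that is P(F(1, 18) > 2.776) = 11.3%; for n = 40 it is 10.8%.

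**Step 5: UVH.** With k = 2 there is one contrast, so ε = 1 and the simulated size is 5.1%, which is nominal within simulation error.

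**The case against.** The strongest objection is that the documents show silence, not an inflated test. A reader might infer that the BVH and post-concussion tests will exceed a nominal 5%. That needs two things the documents do not establish: that the uncorrected univariate F is used, and that sphericity fails. An adjusted or multivariate test also fits the phrase repeated-measures ANOVA, no covariances are given, and 5% is not a level the SAP sets. This objection stands, and the conclusion is therefore conditional.

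A reader might also infer that visit-by-visit intervals will be wrong. Step 1 shows why: a pooled variance of 0.317 is too small for 0 versus 12 weeks (0.542) and too large for 8 versus 12 (0.20). But the SAP plans no visit contrasts and no intervals, so this matters only if such contrasts are added.

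Finally, the effect is small beside the multiplicity. The Description lists six balance and functional measures and no primary outcome. In two diagnoses that makes 12 tests and, if they were independent at an assumed 5%, a chance of 1 − 0.95¹² ≈ 46% of at least one false positive. That stands as a limit on severity. It is no reason to leave each test's own error rate uncontrolled when the remedy costs so little.

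**Conclusion.** The point holds as an omission with a conditional consequence. For BVH and post-concussion, the SAP names a four-visit repeated-measures ANOVA and leaves the handling of non-sphericity open. If the standard uncorrected F is used, the arm-by-time test at an assumed 5% level runs at 5% under sphericity, at 5.2% when the departure is slight, and at about 5.5–9% under the other assumed patterns. The theoretical ceiling of about 11% is a bound, not an expectation. The higher figures depend on a weakly correlated baseline or strongly diverging recovery, each of which is one assumed scenario. In the table the size barely changes between 10 and 40 per arm, so recruiting more subjects would not remove the problem.

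The level, sample sizes and correlations are all assumptions. UVH is unaffected. The importance is minor to moderate: the plan should be changed, but this gap alone would not invalidate the trial.

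**What to change.** State in the SAP that the BVH and post-concussion arm-by-time tests use a mixed model for repeated measures with arm, visit and their interaction, unstructured visit covariance and small-sample degrees of freedom (for example Kenward-Roger), and state the significance level.

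The mixed model is the better choice here because the Description lets subjects skip any test on any day. A classical ANOVA normally needs all four visits, while the mixed model keeps subjects with partial data, on the assumption that skipping is explained by the data observed.

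If the classical ANOVA is kept, state that the Greenhouse-Geisser correction always applies, without a preliminary sphericity test. If visit-specific contrasts are reported, each should use its own variance and not the pooled repeated-measures error.

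The cost is one or two sentences. If sphericity does hold, p-values are slightly larger and a little power is lost: Greenhouse-Geisser then runs at about 4.0–4.7% (3.8–4.9% across the individual settings tabulated) instead of 5%.

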Subjects in the three intervention groups will be asked to perform the same type of exercises as the usual rehabilitation group, but using a virtual reality device that will be issued to the patient for home use. Subjects will use a custom designed program to perform the exercises using a commercially available virtual reality device (no specialized hardware or additions to the commercially available device will be performed). Subjects will be instructed on the first day in how to operate the Virtual Reality Vestibular Rehabilitation (VRVR) program and how to properly perform the exercises. The VRVR device and software will simulate a virtual reality 'room' with an 'X' fixed in front of a wall. Six different background complexities will be offered: 1) plain grey wall, 2) checker board wall, 3) tight houndstooth wall, 4) visual flow from top to bottom, 5) visual flow to the direction of hypofunction, and 6) visual flow moving away from the nose bilaterally. Exercise sessions will start seated upright in a chair and will progress to standing per the home exercise protocol. The system will prompt the patient to begin the exercise and will automatically log the frequency and duration of exercise performed. The system will ask the patient to rate the severity of their symptoms on a 0-10 scale before and after each bout of exercise. Subjects' instruction regarding initial dose and progression will be identical to those given in the usual rehabilitation group. In addition to the general satisfaction survey given to the usual rehabilitation group, Subjects in the intervention group will also be asked to complete a survey regarding comfort, usability, and satisfaction with the VR instrument and with the VRVR software. Subjects will be asked to bring their device with them to their 4 week, 8 week, and 12 weeks appointment to transfer their de-identified data and to insure integrity of the data and device. Subjects will be asked to return the device at the end of the intervention period.

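### The SAP gives unilateral vestibular hypofunction a four-level time factor (0, 4, 8 and 12 weeks), but both of its arms are assessed only at weeks 0 and 4; the repair is evident, and week-4 ANCOVA is the better two-visit analysis

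*Combined protocol and SAP*

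**What the plan says.** The Statistical Analysis Plan section sets one two-way repeated-measures ANOVA for the functional outcomes "for each assessment time (0,4,8, and 12 weeks) for each group of Unilateral Vestibular Hypofunction", and continues the list with BVH and post-concussion. Each diagnosis is compared with its own controls. These are apparently the usual-rehabilitation arms, since the healthy controls attend only once. No exception is made for UVH.

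The Description section says that "those with Unilateral Vestibular Hypofunction (UVH) will be asked to perform a 4-week intervention", and gives the other two diagnoses 12 weeks. It keeps the two lengths apart again when it asks for physical therapy visits "at least one time per week throughout the 4- or 12-week period". In the group and visit table, both UVH arms have the entry "1) Initial Evaluation 2) 4-Weeks post". All BVH and post-concussion arms have the initial evaluation and weeks 4, 8 and 12.

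Two other sentences in the Description mention weeks 8 and 12 without separating the diagnoses. One covers the surveys ("at weeks 4, 8 and 12, surveys would ask about patient comfort and level of satisfaction"). The other has device data transferred at "their 4 week, 8 week, and 12 weeks appointment".

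**The concern.** For one of the three randomised comparisons, the time points in the analysis sentence do not match the data that the schedule will produce. The analyst has to go to the visit table to find the UVH model, although fixing the model is the SAP's job.

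A second issue is one of efficiency and is not caused by the mismatch. Once the time levels are corrected, UVH has a single post-baseline visit. The default analysis then becomes a comparison of raw change scores, which uses the baseline less well than adjusting for it usually does. The baseline score is already collected, so the choice affects precision only.

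**Working it through.** **1. Stated time factor against the schedule.** The SAP lists 4 time levels. With 2 arms and k levels there are 2k cells, and the arm-by-time interaction has (2 - 1)(k - 1) df.

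| Diagnosis | Scheduled weeks | Levels | Cells filled, of the 8 implied | Interaction df: SAP / schedule |
|---|---|---|---|---|
| UVH | 0, 4 | 2 | 4 | 3 / 1 |
| BVH | 0, 4, 8, 12 | 4 | 8 | 3 / 3 |
| Post-concussion | 0, 4, 8, 12 | 4 | 8 | 3 / 3 |

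The SAP's four levels are reproduced for BVH and post-concussion but not for UVH. No assumed figure enters this step.

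**2. What the schedule supports for UVH.** A 2 x 2 model has 4 cell means and all 4 cells are filled, so every parameter is estimable. With two time levels, the interaction F equals the square of the two-sample t statistic on the week 0 to week 4 change. In a simulated data set with 15 per arm, both were 0.0290.

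**3. Change score against ANCOVA.** The documents give no SD, correlation or UVH sample size, so the inputs here are assumptions: correlation rho of 0.5, 0.6 and 0.7 between baseline and week 4, and k, now the ratio of the week-4 SD to the baseline SD.

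In large samples the variance ratio, change score over ANCOVA, is (1 + 1/k² - 2 rho/k) / (1 - rho²). At k = 1 this reduces to 2/(1 + rho):
- rho 0.5: 2/1.5 = 1.333
- rho 0.6: 2/1.6 = 1.250
- rho 0.7: 2/1.7 = 1.176

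In small samples, estimating the slope inflates the ANCOVA variance by 1 + 1/(2n - 4) with n per arm. The factor is 1 + 1/16 = 1.0625 at n = 10 and 1 + 1/36 = 1.0278 at n = 20. Dividing by it gives:

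| Setting | rho 0.5 | rho 0.6 | rho 0.7 |
|---|---|---|---|
| k = 1, large sample | 1.333 | 1.250 | 1.176 |
| k = 1, n = 20 per arm | 1.297 | 1.216 | 1.145 |
| k = 1, n = 10 per arm | 1.255 | 1.176 | 1.107 |
| k = 0.8, n = 10 per arm | 1.647 | 1.563 | 1.499 |
| k = 1.25, n = 10 per arm | 1.054 | 1.000 | 0.960 |

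An example from the last row, at rho 0.7: (1 + 0.64 - 1.12)/0.51 = 1.020, and 1.020/1.0625 = 0.960.

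A simulation of 40,000 trials per setting at k = 1 gave 1.255, 1.178 and 1.102 at 10 per arm, and 1.305, 1.211 and 1.145 at 20, in line with the formula.

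Confidence-interval width goes with the square root. At 10 per arm and k = 1, the change-score interval is 12%, 8% and 5% wider (1.120, 1.085, 1.052). This ignores the one residual df that ANCOVA uses (17 against 18 at 10 per arm).

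**4. Where the gain can vanish.** The numerator of the large-sample ratio equals (1/k - rho)² + (1 - rho²), so that ratio is never below 1. A loss can come only from the small-sample factor, and it appears when the week-4 SD exceeds the baseline SD enough to bring 1/k close to rho.

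**The case against.** The strongest reply is that the documents already resolve the mismatch. The SAP speaks of each assessment time, and the table after it assigns those times by diagnosis. The Description explains why the UVH course is shorter. The next comparison in the SAP uses the final day of treatment, which fits either length. The bracketed weeks can therefore be read as the union over diagnoses, with a valid 2 x 2 analysis for UVH. This largely stands: it settles the likely intent and limits the consequence. But the sentence lists fixed weeks, names UVH and does not state that intent.

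A reader might infer more than the documents support in three ways:
- **That UVH participants would be lost.** A complete-case four-level analysis would indeed keep none. But no week 8 or 12 UVH assessments are scheduled, so the problem would be obvious at once, and a model on the observed visits has two levels.
- **That UVH is meant to be assessed at weeks 8 and 12.** The survey and device sentences schedule no functional assessment. The plan also says "Subjects will be asked to return the device at the end of the intervention period", which is week 4 for UVH.
- **That the mismatch carries into the regression on "the relationship between the exercise parameters and changes in outcome measures".** The SAP does not say whether that model pools diagnoses or which interval the change covers, so no error can be shown.

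It is also fair to object that ANCOVA is a separate preference, that the 2 x 2 interaction is a valid test of a randomised comparison, and that every input to the variance figures is assumed. All of that is right. The case for ANCOVA is precision at almost no cost. A further fair point is that it would give UVH a different estimator from the other two diagnoses.

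**Conclusion.** The mismatch is certain and rests on the text alone: two of the four stated time points do not exist for either UVH arm, while BVH and post-concussion match the SAP. Its consequence is small. It is a specification error with an evident repair, and it does not make UVH unanalysable or bias its comparison.

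The ANCOVA recommendation is well founded, but its size is conditional. With equal SDs and rho of 0.5 to 0.7, the change-score variance is about 33% to 18% larger in large samples and 26% to 11% larger at 10 per arm. At 10 per arm the excess is 65% to 50% if the week-4 SD is 0.8 times baseline, and from 5% down to -4% if it is 1.25 times baseline. A gain is therefore likely but not guaranteed in a very small sample.

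**What to change.** 1. In the Statistical Analysis Plan, state the time levels by diagnosis, as in the visit table: UVH at 0 and 4 weeks; BVH and post-concussion at 0, 4, 8 and 12 weeks.
2. Specify the UVH comparison of virtual reality with usual rehabilitation as the week-4 score analysed by ANCOVA, with arm as factor and the baseline score of the same measure as covariate.
3. Either say that the UVH estimator differs from the other two diagnoses, or use baseline adjustment there as well.
4. Reconcile the survey and device-transfer wording in the Description with the UVH visit schedule. This is clarification only.

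The cost is one or two sentences in the SAP and a clause in each of the two Description sentences. Visits, participants and data collection do not change. The statistical price is one residual degree of freedom and, if step 3 is met by disclosure only, estimators that are not uniform across diagnoses.

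### The final-day comparison with non-randomised healthy volunteers makes no allowance for age and gives no estimate of any group's distance from healthy, so an age gap could bias it in either direction

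*Combined protocol and SAP*

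**What the plan says.** Under the Statistical Analysis Plan heading, a one-way ANOVA is to "compare functional outcome measures of all groups on the final day of treatment only to healthy control performance". Group is the only factor and no covariate is named.

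The Description randomises patients only between usual rehabilitation and the virtual reality intervention, within each of three diagnoses. It then adds the comparison group: "Additionally, there will be a seventh group consisting of healthy control subjects that have no history of vestibular symptoms". That is the only criterion given for these volunteers. They are recruited through public notices, email lists and personal contact, and are seen once. On their tests the Description says: "This healthy control group will perform the same tests as the other groups perform on Day 1". Their purpose is also stated: "This group will be used to compare outcomes of usual rehabilitation and intervention groups, to the function of those without disorders of vestibular function".

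The plan does look at age. "Similarities in subject group characteristics will be determined using a one-way ANOVA", and "Characteristics will include: Age, height, weight, questionnaire scores, and functional outcome scores". It does not say what happens if the groups differ, or whether the healthy group is part of that check.

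**The concern.** The benchmark is meant to show how far treated patients remain from people without a vestibular disorder. Randomisation does not help here, because the volunteers come from a different source. If they are younger than the patients and an outcome worsens with age, part of the age effect reads as residual deficit. If they are older, a real deficit can be hidden.

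Age is already among the characteristics to be tested, yet the result of that test has no consequence. Any adjustment would therefore be chosen after the data are seen.

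The form of the test is a second weakness. An omnibus F-test over all groups says only that some means differ. It does not estimate any patient group's difference from healthy, and it can be significant because patient groups differ from one another.

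**Working it through.** **Inputs.** The documents give no ages, SDs, group sizes, significance level or age-outcome relation, so there is no stated figure to reproduce. From the documents: seven groups, one-way ANOVA, no covariate. Assumed: equal groups of 10 to 30, two-sided 5% level, normal data with within-group SD 1, r from 0.2 to 0.6, and an age gap g from 0.5 to 1.5 age SDs with only the controls shifted.

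**Bias.** Shift in the patient-healthy difference: d = r × g. This runs from 0.2 × 0.5 = 0.1 to 0.6 × 1.5 = 0.9 outcome SDs, with a sign that depends on which side is older.

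**False significance of the planned F-test, no true deficit.** With one of seven groups shifted by d, the noncentrality is λ = n × d² × 6/7, on 6 and 7(n − 1) degrees of freedom. At n = 20 the critical F is 2.17.

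| n per group | r | gap | d | λ | Falsely significant |
|---|---|---|---|---|---|
| 20 | 0.2 | 0.5 | 0.1 | 0.17 | 6% |
| 20 | 0.6 | 0.5 | 0.3 | 1.54 | 12% |
| 20 | 0.4 | 1.0 | 0.4 | 2.74 | 18% |
| 20 | 0.6 | 1.5 | 0.9 | 13.89 | 79% |
| 10 | 0.4 | 1.0 | 0.4 | 1.37 | 11% |
| 30 | 0.4 | 1.0 | 0.4 | 4.11 | 27% |

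**Masking.** Take a true deficit of 0.6 SD in all six patient groups and n = 20. With no age gap, λ = 20 × 0.36 × 6/7 = 6.17 and the F-test is significant in 40% of studies. With controls 1 SD older, the visible difference is 0.6 − r. For r = 0.4 it is 0.2 SD (λ = 0.69, 8%). For r = 0.6 it is zero (5%).

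**Would the age check reveal the gap?** The same formula applies with g in place of d, provided the controls are in that test and they alone differ in age.

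| Age gap | n = 10 | n = 15 | n = 20 | n = 30 |
|---|---|---|---|---|
| 0.5 SD | 14% | 21% | 28% | 42% |
| 1.0 SD | 52% | 74% | 88% | 98% |

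A moderate gap would usually be missed. A large one would usually be seen at 20 or more per group, but the plan attaches no action to it.

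**Does simple age adjustment solve it?** Only if the age slope is the same in patients and controls. Suppose instead that the controls' slope is flat and patients equal healthy people of their own age. The pooled slope is then 6/7 of the patients' slope, so a common-slope model shifts the difference by 6/7 × r × g: 0.09, 0.34 and 0.77 SD for (0.2, 0.5), (0.4, 1.0) and (0.6, 1.5). In simulations of six Dunnett contrasts at 20 per group, that model gave at least one false signal in 6%, 24% and 79% of studies, while unadjusted contrasts stayed at 5%. Separate slopes evaluated at the patients' mean age gave no shift and 5% to 7%. A test for unequal slopes rejected in only 14%, 41% and 77%, so it is not a safe way to choose the model.

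**The case against.** **The age link is not documented.** Nothing in the protocol says that any outcome varies with age, and every input above is assumed. This stands. A range of 6% to 79% shows mainly that the answer depends on the assumptions, and its top pairs the largest r with the largest gap.

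**Higher error rates might be inferred.** At the same inputs, six separate Dunnett comparisons with healthy give at least one false signal in about 30% (0.4, 1.0) and 91% (0.6, 1.5) of studies. Those rates do not belong to this plan, which specifies a one-way ANOVA and no such contrasts.

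**The outcome set might be thought undefined.** The Description says: "Balance and functional outcome measures will include the Dizziness Handicap Inventory (DHI), Visual Analog Score (VAS) of symptoms", whereas the SAP lists questionnaire scores apart from functional scores. The table at the end largely settles this. It puts the symptom and confidence scales under a questionnaire heading, and the Functional Gait Assessment and modified CTSIB under a functional heading. The table is broken in the text read, but its split agrees with the SAP. A sentence of clarification is enough.

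**Adjustment can do harm.** This also stands, as the flat-slope case shows. It argues for a carefully specified adjustment beside the unadjusted result, and not for leaving age out.

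**Conclusion.** The gap is real: a non-randomised benchmark, no age range or matching, no covariate, no consequence of the age check, and a test that estimates no group's distance from healthy. The possible bias is r × gap, or 0.1 to 0.9 outcome SD over the assumed range. Its actual size and direction are unknown.

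A reader might infer that the volunteers will be younger, or that the benchmark will overstate residual deficit. The documents give no ages and support neither. A reader might also infer that the trial's treatment comparison is compromised. It is not: the randomised comparisons within diagnosis and the regression on exercise parameters do not use the healthy group.

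Severity is minor to moderate, with medium confidence. The point should be addressed because prespecifying costs little and removes a choice that would otherwise be made after seeing the data.

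**What to change.** Keep the planned unadjusted comparison and add the following to the SAP, to apply whatever the age check shows:

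- For the outcomes under the table's functional heading, such as the Functional Gait Assessment and modified CTSIB, report six patient-versus-healthy differences, adjusted for age, with Dunnett-adjusted 95% confidence intervals. State that these are the outcomes the benchmark covers.
- Name one main adjusted estimate in advance: separate age slopes for patients and controls, evaluated at an age within their overlap. No slope test chooses the model.
- Report the age distributions and their overlap. Where overlap is poor, or controls show little spread on a scale, report the unadjusted difference with that caveat. Say beforehand how both conditions will be judged.
- State that a non-significant difference will not be read as normal function.

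**Cost.** SAP wording and a few degrees of freedom; no extra subjects, and age is already to be analysed. Precision is limited. At an assumed 20 per group, the unadjusted Dunnett half-width is 2.60 × √(2/20) = 0.82 SD. In the simulated settings it was 0.66 to 0.82 SD with a common slope and 0.72 to 1.16 SD with separate slopes. The adjusted result depends on age overlap: with normal ages and equal SDs, 2Φ(−g/2) gives 80%, 62% and 45% at gaps of 0.5, 1.0 and 1.5 SD. Other differences between volunteers and patients remain.
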